#### 5.4.3 Colony Stimulating Agents

Under no circumstances are potential participants to be treated with colony stimulating agents (CSA) during Step 1 to elevate hematology laboratory parameters to facilitate entry into Step 2 of the study. CSAs, such as erythropoiesis-stimulating agents or granulocyte colony-stimulating factor, will not be provided by the study.

## 6.0 CLINICAL AND LABORATORY EVALUATIONS

## 6.1 Schedule of Evaluations (SOE)

Table 6.1-1: SOE: Step 1 - Study Visits for 4-week Treatment and Post-Treatment Follow-up

Evaluation	Screening	Entry (Day 0)	On Treatment		Treatment Completion	Post-treatment					HCV Recurrence/ Virologic Failure Confirmation (see Event-Driven Evaluations in section 6.2.4 )	HIV-1 Virologic Breakthrough Confirmation( see Event-Driven Evaluations in section 6.2.4 )	Premature Study and /or Treatment Discontinuation Evaluations				
			Weeks; See section 6.2.3 for study windows														
			1	2		4	8	12	14	16/SVR12	28						
Documentation of HIV-1 (if applicable)	X																
Documentation of Acute HCV Infection	X																
Documentation of Cirrhosis Status	X																
Documentation of Historical Labs (see section 6.3.4 )	X																
Medical History	X																
Medication History	X	X															
Clinical Assessments (see section 6.3.7 )	X	X	X	X	X	X	X	X	X	X	X	X	X	X			
Hematology	X	X									X						
Chemistries	X	X	X	X	X	X	X	X	X	X	X			X			

Evaluation	Screening	Entry (Day 0)	On Treatment		Treatment Completion	Post-treatment					HCV Recurrence/ Virologic Failure Confirmation (see Event-Driven Evaluations in section 6.2.4 )	HIV-1 Virologic Breakthrough Confirmation (see Event-Driven Evaluations in section 6.2.4 )	Premature Study and /or Treatment Discontinuation Evaluations	
			1	2		4	8	12	14	16/SVR12	28			
			Weeks; See section 6.2.3 for study windows											
Liver Function Tests (LFTs)	X	X	X	X	X	X	X	X		X	X	X		X
Calculated CrCl	X	X			X					X	X	X		X
Coagulation Markers	X	X		X	X	X				X		X		X
Urine Sample for Substance Use Screen		X	X	X	X	X	X	X		X	X	X		X
FSH	X													
Pregnancy Testing	X	X	X	X	X	X	X			X	X	X		X
Serologies	X					X (see section 6.3.8 )					X			
HCV Antibody	X					X (see section 6.3.8 )								
CD4+/CD8+ (for participants with HIV-1 infection)	X	X			X					X				X
Stored Plasma and PBMC for Immunologic Studies	X	X			X		X			X	X	X		X
Plasma HCV RNA (screening performed at local lab, see section 6.3.10 )	X													
Plasma HCV RNA (real-time, see section 6.3.10 )		X	X	X	X	X	X	X		X	X	X		X

Evaluation	Screening	Entry (Day 0)	On Treatment		Treatment Completion	Post-treatment					HCV Recurrence/ Virologic Failure Confirmation (see Event-Driven Evaluations in section 6.2.4 )	HIV-1 Virologic Breakthrough Confirmation (see Event-Driven Evaluations in section 6.2.4 )	Premature Study and /or Treatment Discontinuation Evaluations	
			1	2		4	8	12	14	16/SVR12	28			
			Weeks; See section 6.2.3 for study windows											
Plasma HCV Genotype (screening performed at local lab unless unavailable, see section 6.3.10 )	X											X		
Plasma HIV-1 RNA (for participants with HIV-1 infection) (real-time, see section 6.3.10 )	X	X			X							X	X	X
Stored Serum for HIV-1/HCV Studies (see section 6.3.10 )	X	X	X	X	X	X	X			X	X	X	X	X
Stored Plasma for HIV-1/HCV Studies (see section 6.3.10 )			X	X		X	X			X	X	X	X	X
Plasma for PK Testing (see section 11.2 )		X	X	X	X	X	X			X		X	X	X
Dried Blood Spots (DBS) for PK (see section 11.2 )		X			X					X		X	X	X
Optional Hair Sampling for PK (see section 11.2 )		X			X					X		X	X	X

Evaluation	Screening	Entry (Day 0)	On Treatment		Treatment Completion	Post-treatment					HCV Recurrence/ Virologic Failure Confirmation (see Event-Driven Evaluations in section 6.2.4 )	HIV-1 Virologic Breakthrough Confirmation (see Event-Driven Evaluations in section 6.2.4 )	Premature Study and /or Treatment Discontinuation Evaluations	
			1	2		4	8	12	14	16/SVR12	28			
			Weeks; See section 6.2.3 for study windows											
IL-28B Genotype and HLA Typing		X			X	X								
Pregnancy Prevention Counseling	X	X			X	X						X		X
Adherence Assessments (see section 6.3.14 )		X	X	X	X									X
Study Drug Dispensing/First Dose Observed		X												
Risk Factor Assessment		X	X	X	X	X				X	X			
Health Outcomes Questionnaire (EQ-5D)		X			X					X	X			
Health Care Utilization Questionnaire		X			X					X	X			
Reinfection Prevention Counseling		X			X	X				X	X			
Collection and Updating of Locator Information		X			X	X	X							
Remote Contact Reminder for Week 16 Visit								X						

Table 6.1-2: SOE: Step 2- Repeat Treatment for Suspected Relapse/Virologic Failure/Post-treatment Viremia or Re-infection

Evaluation	Re-Treatment Entry/Initiation	On-Retreatment (Weeks) R = Step 2 Entry ReTx=Retreatment					Post-Retreatment		HCV Recurrence/Virologic Failure (see Event Driven Evaluations in section 6.2.4 ) Confirmation	HIV-1 Virologic Breakthrough Confirmation (see Event-Driven Evaluations in section 6.2.4 )	Premature Study and /or Treatment Discontinuation Evaluations
		R+2 (RBV regime ns only)	R+4	R+8	R+12 (12 & 16 weeks ReTx only)	R+16 (16 weeks ReTx only)	SVR12 visit (R+20, R+24 or R+28, depending on re-treatment duration)	Only for RBV exposed (R+32, R+36 or R+40, depending on re-treatment duration)			
		See section 6.2.3 for study windows									
Evaluation of Step 2 Entry Requirements (see section 6.3.20 )	X										
Clinical Assessments (see section 6.3.7 )	X	X	X	X	X	X	X	X	X		X
Hematology, Chemistries	X	X	X	X	X	X	X		X		X
LFTs (see section 6.3.8 )									X		
Serologies (see section 6.3.8 )	X								X		
Calculated CrCl (if on RBV)	X	X	X	X	X	X					X
Pregnancy Testing (see section 6.3.8 )	X	X	X	X	X	X	X	X			X

Evaluation	Re-Treatment Entry/ Initiation	On-Retreatment (Weeks) R = Step 2 Entry ReTx=Retreatment					Post-Retreatment		HCV Recurrence/Virologic Failure (see Event Driven Evaluations in section 6.2.4 ) Confirmation	HIV-1 Virologic Breakthrough Confirmation (see Event-Driven Evaluations in section 6.2.4 )	Premature Study and /or Treatment Discontinuation Evaluations	
		R+2 (RBV regime ns only)	R+4	R+8	R+12 (12 & 16 weeks ReTx only)	R+16 (16 weeks ReTx only)	SVR12 visit (R+20, R+24 or R+28, depending on re- treatment duration)	Only for RBV exposed (R+32, R+36 or R+40, depending on re- treatment duration)				
See section 6.2.3 for study windows												
CD4+/CD8+ (for participants with HIV-1 infection)	X			X			X	X				X
Stored Plasma and PBMC (see section 6.3.9 )	X		X		X		X	X		X		X
Plasma HCV RNA (real-time, see section 6.3.10 )	X	X	X	X	X	X	X			X		X
Plasma HCV Genotype (see section 6.3.10 )										X		
Plasma HIV-1 RNA (for participants with HIV-1 infection, real-time, see section 6.3.10 )			X	X	X	X	X			X	X	X
Stored Serum for HIV-1/HCV Studies (see section 6.3.10 )		X	X	X	X		X			X	X	X

Evaluation	Re-Treatment Entry/ Initiation	On-Retreatment (Weeks) R = Step 2 Entry ReTx=Retreatment					Post-Retreatment		HCV Recurrence/Virologic Failure (see Event Driven Evaluations in section 6.2.4 ) Confirmation	HIV-1 Virologic Breakthrough Confirmation (see Event-Driven Evaluations in section 6.2.4 )	Premature Study and /or Treatment Discontinuation Evaluations	
		R+2 (RBV regime ns only)	R+4	R+8	R+12 (12 & 16 weeks ReTx only)	R+16 (16 weeks ReTx only)	SVR12 visit (R+20, R+24 or R+28, depending on re- treatment duration)	Only for RBV exposed (R+32, R+36 or R+40, depending on re- treatment duration)				
See section 6.2.3 for study windows												
Stored Plasma for HIV-1/HCV Studies (see section 6.3.10 )		X	X	X	X			X		X	X	X
Plasma for PK Testing (see section 11.2 )		X	X	X						X	X	X
Pregnancy Prevention Counseling	X	X	X	X	X	X	X					X
Study Drug Dispensing	X		X	X	X							
Risk Factor Assessment	X	X	X	X	X	X	X	X				
Reinfection Prevention Counseling	X					X	X					X

## 6.2 Timing of Evaluations

### 6.2.1 Screening Evaluations

Screening evaluations must occur prior to the participant starting any study medications, treatments, or interventions.

For Step 1, screening evaluations to determine eligibility must be completed within 28 days prior to entry unless otherwise specified. For Step 2, participants can enter Step 2 up to 56 days after the confirmatory HCV RNA sample date completed as part of Step 1.

In addition to data being collected on participants who enroll into the study, demographic, clinical, and laboratory data on screening failures will be captured in a Screening Failure Results form and entered into the ACTG database.

### 6.2.2 Entry Evaluations

Entry evaluations must occur at least 24 hours after screening evaluations unless otherwise specified. For Step 1, participants must begin treatment within 24 hours after registration and upon completion of entry evaluations. The first dose of G/P will be provided to the participant and taking the first dose will be observed by study staff.

For participants entering Step 2, treatment must be started within 72 hours of Step 2 entry.

### 6.2.3 Post-Entry Evaluations

All post-entry evaluations occur in reference to the start of study therapy.

#### On-Treatment Evaluations

Study visits must be scheduled on the weeks indicated in [Tables 6.1-1](#) and [6.1-2](#), within the visit windows described below, as appropriate for the visit.

##### Step 1:

- Weeks 1 and 2 have a window of  $\pm 3$  days.
- Week 4 has a window of -7 days and +14 days.

##### Step 2:

- Week R+2 has a window of  $\pm 3$  days.
- Weeks R+4, R+8, R+12, and R+16 have a window of -7 days and +14 days.

### Treatment Completion Evaluations

Clinical assessment and laboratory evaluation, as outlined in [section 6.1](#), will be performed at treatment completion (Step 1: week 4, Step 2: week R+8, R+12, or R+16).

### Post-Treatment Evaluations

Following treatment completion, participants will undergo evaluations as outlined in [Tables 6.1-1](#) and [6.1-2](#), within the study windows, as indicated below.

After the last dose of study drugs, the post-treatment study visits have the following windows:

#### Step 1:

- Study weeks 8, 12, and 16: -5 days and +21 days
- Study week 28: -7 days and +28 days

#### Step 2:

- Study week R+20, R+24, or R+28 (12 weeks after re-treatment completion for those not receiving RBV depends on Step 2 treatment duration): -5 days and +28 days
- Study week R+32, R+36, or R+40 completion (for those receiving RBV): -14 days and + 28 days

#### 6.2.4 Event-Driven Evaluations

##### HCV Viral Recurrence/Virologic Failure

In Step 1, all cases of confirmed HCV recurrence/virologic failure occurring before or at the week 16/SVR12 visit will undergo evaluation for preliminary determination of suspected relapse versus re-infection (see [Table 6.1-1](#), A5380 MOPS, and A5380 Laboratory Processing Chart [LPC]). Viral recurrence is defined as confirmed HCV RNA value >LLOQ after achieving HCV RNA <LLOQ (TD or TND). Virologic failure is defined as failure to achieve HCV RNA <LLOQ (TD or TND) and confirmed increase in HCV RNA >1 log10 from nadir. These participants will enter Step 2. This confirmatory sample should be collected within 56 days of Step 2 entry.

Participants should have this confirmatory evaluation done, per [Table 6.1-1](#), before initiation of Step 2 therapy. Participants should be re-tested with HCV RNA and hepatic panel (LFTs) as soon as possible after viral recurrence or virologic failure to confirm the HCV RNA >LLOQ or >1 log10 from nadir, respectively.

If HCV RNA is >1000 IU/mL, as part of Step 2 entry, each available post-treatment viremic sample will be sent for HCV genotyping and RAS analysis. A stored baseline sample will also be sent for RAS analysis. Results from these assessments will be delivered to the A5380 CMC via email

([[contact]](mailto:[contact])) by the designated Virology Specialty Laboratory (VSL) and initial determination of suspected relapse versus re-infection will be made. If HCV RNA is persistently less than or equal to 1000 IU/mL, the participant may still meet the criteria of virologic failure and/or post-treatment HCV viremia described in [section 4.3.1](#).

Results of repeat HCV genotype and RAS analysis will be delivered to the A5380 CMC ([[contact]](mailto:[contact])). If the genotype/subtype has switched, this will be classified as a re-infection. If the same genotype/subtype and there are emergent RASs, this will be initially classified as a suspected relapse. For other situations (e.g., same genotype/subtype without emergent RASs), the classification will be determined later by phylogenetic analysis (with samples sent from the repository, see virologic studies in [section 6.3.10](#)), but for Step 2 these will be classified as “undefined post-treatment viremia” but treated as a suspected relapse. Per [section 6.3.8](#), HAV IgM, HBc IgM Ab, total HBcAb, and HBsAg will be done during the Event-driven Evaluations outlined in the SOE with results available prior to Step 2 entry.

Following determination of suspected relapse versus re-infection versus undefined post-treatment viremia, a member of the A5380 CMC will contact the site coordinator and site PI to discuss the re-treatment approach for the participant.

For all participants with recurrence of the same genotype/subtype, stored samples from the repository will be batched and sent for sequencing, phylogenetic analysis, and definitive determination of relapse versus re-infection (see virologic studies in [section 6.3.10](#)). Suspected relapse or undefined post-treatment viremia may then be reclassified as confirmed relapse or re-infection for the purposes of [exploratory objective 1.4.1](#).

#### HIV-1 Virologic Breakthrough

In this study, HIV-1 viral breakthrough is defined as follows (this only applies for participants on ART):

Among participants with HIV-1 RNA <50 copies/mL at study entry, a confirmed increase to ≥200 copies/mL at any time after entry into Step 1 and Step 2.

The increase in plasma HIV-1 RNA should be confirmed with repeat central or local testing as soon as possible (not to exceed 4 weeks); see HIV-1 Virologic Breakthrough Confirmation in [Tables 6.1-1](#) and [6.1-2](#). For participants with confirmed HIV-1 viral breakthrough (≥200 copies/mL), a plasma specimen should be sent for HIV genotyping and sent to the designated A5380 VSL for evidence of HIV-1 drug resistance. Results will be reported back to sites in real-time from the designated A5380 VSL. See [section 6.3.10](#), Stored Serum and Plasma for HIV-1/HCV Studies.

Clinical management of HIV-1 virologic breakthrough and treatment failure will be

handled by local site PI according to current HIV treatment guidelines and local standard of care. The A5380 CMC should be contacted before switching ART.

HCV medications should be continued unless safety events warrant the discontinuation of these medications, as outlined in [section 8.1](#) of the protocol.

These criteria only apply to participants currently on ART treatment. They do not apply to participants meeting the ART untreated parameters outlined in [section 4.1](#).

#### 6.2.5 Study Completion Evaluations

For those not proceeding to Step 2, the final study visit occurs at study week 28.

For those proceeding to Step 2, the final study visit occurs 12 weeks after re-treatment completion, with extension to 24 weeks after re-treatment completion if the participant receives RBV.

#### 6.2.6 Discontinuation Evaluations

Evaluations for Registered Participants Who Do Not Start Study Treatment  
All eCRFs must be keyed for the period up to and including the entry visit.

##### Premature Treatment Discontinuation Evaluations

The A5380 CMC must be informed, as soon as possible, when a participant comes off study treatment due to an AE. Participants who permanently discontinue study treatment for toxicity or any other reason, and who have not met the HCV virologic failure criteria below, will also follow the schedule in [Table 6.1-2](#). If applicable, additional or more frequent post-treatment toxicity follow-up may be determined by the site PI.

Participants who prematurely discontinue study treatment (i.e., prior to completion of the last dose of G/P per the assigned dosing period) will complete the premature treatment discontinuation evaluations. Participants will then follow the post-treatment schedule in [Table 6.1-2](#).

NOTE: In Step 2 where applicable: If G/P is discontinued, participants should discontinue RBV. Under no condition should the participant remain on RBV monotherapy. In contrast, participants who discontinue RBV in Step 2 can continue G/P to complete their planned G/P regimen.

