## 3.0 STUDY DESIGN

A5380 is a phase II single-arm, open-label study to assess the efficacy of FDC G/P in acute HCV-infected participants, with and without HIV-1 coinfection, given for 4 weeks. This study will assess whether G/P confers successful treatment, superior to a cure rate of 80%. The study will entail 2 steps: Step 1—treatment of acute infection with 4 weeks of G/P, and Step 2—re-treatment of participants experiencing post-treatment viremia in Step 1 with 8-16 weeks of G/P with or without RBV with modifications to the retreatment regimen allowed at the discretion of the site PI after discussion with the A5380 CMC.

Prospective participants will be enrolled in Step 1 if diagnosed with acute infection, defined below in [section 4.1.3](#). Both HIV infected and HIV uninfected participants will be included, and participants with HIV who are taking protocol-defined compatible ARVs, as per discretion of the local provider. A minimum of 10 participants with HIV will be enrolled.

Step 1 post-treatment follow-up visits for all participants will occur at 4, 8, 12, and 24 weeks after the last dose of study drug (FDC G/P).

The primary outcome will be SVR12 (i.e., HCV RNA <LLOQ, either TD or TND, at 12 weeks after end of treatment).

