#### 4.3 Step 2 Inclusion Criteria

- 4.3.1 Ability and willingness of participant to provide written informed consent for Step 2.
- 4.3.2 Completion of Step 1 treatment regimen and meeting any of the below criteria, before or at the week 16 (SVR12) Step 1 visit:

Suspected relapse, defined as HCV RNA <LLOQ (TD or TND) at end of treatment (week 4) or during follow-up, and including confirmation of HCV RNA >LLOQ with the same genotype.

NOTE: Suspected relapse is documented by the email receipt of relapse determination by the designated A5380 team member.

OR

Re-infection, defined as HCV RNA <LLOQ (TD or TND) at end of treatment (week 4) or during follow-up, and including confirmation of HCV RNA >LLOQ with new genotype consistent with a new HCV viral infection.

NOTE: Re-infection is documented by the email receipt of re-infection determination by the designated A5380 team member.

OR

Virologic failure, defined as failure to achieve HCV RNA <LLOQ (TD or TND) and confirmed increase in HCV RNA >1  $\log_{10}$  from nadir.

OR

Post-treatment HCV viremia, defined as HCV RNA >LLOQ at any point after end of treatment (week 4) or during follow-up, not otherwise meeting definition of suspected relapse, re-infection, or virologic failure.

- 4.3.3 Detectable HCV RNA from the confirmatory sample (see [section 6.2.4](#)) collected within 56 days of Step 2 entry.
- 4.3.4 HIV-1 infection status documented as absent or present, as defined below:

For participants self-reporting as HIV-1 negative, HIV-1 infection testing should be performed prior to Step 2 entry via rapid HIV-1 and/or E/CIA test kit.

OR

HIV-1 infection, documented by any licensed rapid HIV-1 test or HIV-1 E/CIA test kit at any time prior to study entry and confirmed by a licensed Western blot or a second antibody test by a method other than the initial rapid HIV-1 and/or E/CIA, OR by HIV-1 p24 antigen, OR documented plasma HIV-1 RNA viral load >LLOQ at any time prior to study entry.

NOTE: The term “licensed” refers to a FDA-approved kit, which is required for all IND studies. For sites that are unable to obtain an FDA-approved kit, a kit that has been certified or licensed by an oversight body within the country and validated internally is acceptable.

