##### HCV Virologic Failure

Participants who experience for HCV virologic failure (see details in [section 6.2.4](#)) in Step 1 will have the option to enter Step 2 for re-treatment, otherwise the participants will be followed on study/off treatment through week 28.

Participants who permanently discontinue study treatment for HCV virologic failure (see details in [section 6.2.4](#)) in Step 2 will be followed through 12 weeks (or 24 weeks, if RBV given) after the treatment completion. No further treatment will be provided by the study.

Virologic evidence of recurrence, defined as HCV RNA  $\leq$ LLOQ at end of treatment but HCV RNA quantifiable ( $>$ LLOQ) during follow-up, will require confirmation and should be performed in real time at the designated VSL as soon as possible but within 2 weeks after determination of initial observation. The results will be provided to the co-chairs and site investigators within 2 weeks of specimen receipt.

#### HCV Virologic Response-Based Treatment Stopping Criteria in Step 2

The following on-treatment HCV virologic response-based treatment stopping criteria will be utilized for all participants in Step 2:

- Confirmed increase in HCV RNA  $>$ LLOQ if HCV RNA previously declined to  $\leq$ LLOQ (detected or not detected) AND
- Confirmed  $\geq 1 \log_{10}$  IU/mL HCV RNA on-treatment increase from nadir
- Confirmation will be required for all stopping criteria and should be performed as soon as possible but within 2 weeks after determination of initial observation (see HCV Recurrence/VF Confirmation in [Table 6.1-2](#)).

HCV RNA measurement to confirm treatment failure will be performed in real-time at the designated VSL and the results will be provided to the site PI within 2 weeks of specimen receipt. If treatment failure is confirmed, then all study treatment should be stopped. However, participants should be followed as per [section 6.2.6](#).

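### Protocol 6.2.6 sends early treatment stoppers to the Step 2 schedule (Table 6.1-2) without limiting this to Step 2, so the instruction cannot work for Step 1

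*Protocol*

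**What the plan says.** The part of Protocol 6.2.6 on premature treatment discontinuation has two sentences about follow-up.

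- The first covers permanent discontinuation for toxicity or any other reason. It says that those who stop "and who have not met the HCV virologic failure criteria below, will also follow the schedule in" Table 6.1-2.
- The second covers anyone who stops before the last G/P dose of the assigned course. After the discontinuation evaluations, "Participants will then follow the post-treatment schedule in" Table 6.1-2.

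Neither sentence names a step, and Table 6.1-1 is not cited in this part. The only step limit is on the separate note about ribavirin.

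Table 6.1-2 is titled "SOE: Step 2- Repeat Treatment for Suspected Relapse/Virologic Failure/Post-treatment Viremia or Re-infection", and its column header defines the time origin as "R = Step 2 Entry ReTx=Retreatment". Table 6.1-1 is the Step 1 schedule. It contains post-treatment weeks 8, 12, 16/SVR12 and 28 and its own premature-discontinuation column.

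Other sections give Step 1 follow-up differently from 6.2.6:

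- Section 3.0: "Step 1 post-treatment follow-up visits for all participants will occur at 4, 8, 12, and 24 weeks after the last dose of study drug".
- Section 6.2.5: "For those not proceeding to Step 2, the final study visit occurs at study week 28".
- Section 8.1.1 makes the Step 1 visits at weeks 8, 12, 16 and 28 mandatory for all participants.

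**The concern.** Section 6.2.6 is where a site would look when a participant stops G/P early. For a Step 1 participant it names a table that has no visit they can attend on a defined date.

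These participants matter to the analysis. Protocol 10.1 keeps everyone who starts treatment in the primary analysis, whatever the reason for stopping. The SAP uses HCV RNA at weeks 8, 12 and 28 for SVR4, SVR8 and SVR24 (SAP 2.3.2). It also allows those visits to bracket a missed week 16 sample (SAP 3.1, footnote). Without a bracket, a missed week 16 sample counts as failure, apart from the SAP's COVID-19 exception. The visit 4 weeks after treatment is also the scheduled safety contact nearest the end of the primary adverse-event window.

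**Working it through.** The plan gives no figure on this point, so the check is mainly a comparison of text. A short calculation of exposure follows.

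**1. Does the instruction reach Step 1?** It covers stopping before the end of the assigned G/P course, and Section 5.0 makes G/P the Step 1 study treatment. Where the protocol means one step, it says so: the ribavirin note in 6.2.6, the virologic failure paragraphs of 6.2.6, and the Step 2 item in 9.1. The post-treatment text in 6.2.3 cites both tables. A silent restriction to Step 2 is therefore not a natural reading. If it were intended, 6.2.6 would give Step 1 stoppers no schedule at all.

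**2. Can a Step 1 stopper use Table 6.1-2?** Its visits run from R+2 to R+40, with R the date of Step 2 entry. Step 2 entry requires "Completion of Step 1 treatment regimen and meeting any of the below criteria". A participant who stopped early has not completed the regimen, so no R date can arise under the criteria.

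**3. Does it conflict with other sections?**

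| Section | Step 1 follow-up given |
|---|---|
| 6.2.6, early stoppers | Table 6.1-2 (counted from Step 2 entry) |
| 3.0 | 4, 8, 12 and 24 weeks after last dose, all participants |
| 8.1.1 | Weeks 8, 12, 16 and 28 |
| 6.2.5 | Final visit at week 28 if not entering Step 2 |
| 6.2.6, virologic failure | See next sentence |

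For Step 1 virologic failures who do not enter Step 2, the same section says "otherwise the participants will be followed on study/off treatment through week 28", which is the Step 1 calendar.

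**4. Is it corrected later?** The changes listed in Letters of Amendment 1 to 4 and Clarification Memos 1 to 3 do not include 6.2.6.

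**5. How many participants could be exposed?** Inputs: N = 44 (Protocol 10.4); 0.1% permanent discontinuation for adverse reactions over 8 to 16 weeks of G/P (Protocol 2.1). The documents give no any-reason stopping rate for Step 1, so 1% to 5% is my assumption. Expected stoppers = 44 × r; chance of at least one = 1 − (1 − r)^44.

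| Rate r | Expected stoppers | Chance of at least one |
|---|---|---|
| 0.1% (documented, adverse reactions only) | 44 × 0.001 = 0.04 | 1 − 0.999^44 = 4.3% |
| 1% (assumed) | 44 × 0.01 = 0.44 | 1 − 0.99^44 = 35.7% |
| 5% (assumed) | 44 × 0.05 = 2.2 | 1 − 0.95^44 = 89.5% |

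These are chances that someone stops. For anyone to be affected, the site must also follow 6.2.6 in preference to 3.0 and 8.1.1. The documents give no basis for a probability of that.

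**6. Does the design depend on the citation?** No. With success defined as 40 or more of 44, the exact one-sided alpha at 80% is 0.044. Power at a true 95% is 0.933, which matches the protocol's 93%. Neither uses the table reference.

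**The case against.** The strongest reply is that the right Step 1 schedule is already in the protocol several times: in 3.0, in the mandatory wording of 8.1.1, in Table 6.1-1 with its own discontinuation column, and in 6.2.3, which cites both tables. Section 6.2.6 also requires the clinical management committee to be told when someone stops for an adverse event, so a central team would see such a case. A site that found Table 6.1-2 unusable would probably turn to Table 6.1-1. One that adapted it would still hold an SVR12 visit. All of this stands, and it makes the harm conditional and small. It does not make the instruction right.

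A reader might infer more than the documents support:

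- *That the primary outcome or power is damaged.* Nothing shows that a site would drop the week 16 visit that 8.1.1 makes mandatory, so counting lost week 16 results as failures would be speculation.
- *That the adverse-event window changes.* SAP 3.1 closes it by elapsed time after discontinuation, although Protocol 10.2.1.2 and SAP section 5, item 10, describe it by the visit. I claim no change to it.
- *That 6.2.5 requires all four Step 1 visits.* It sets only the final one, at week 28.
- *That the correction should also settle how visits are timed.* Section 3.0, the window text in 6.2.3 and Protocol 10.2.1.1 count from the end of treatment. The opening of 6.2.3 counts from the start of therapy, and SAP 4.1 counts from study entry. For someone stopping at week 2, counting from last dose gives study weeks 2 + 4 = 6, 2 + 8 = 10, 2 + 12 = 14 and 2 + 24 = 26, not 8, 12, 16 and 28. Choosing between these is a separate decision.

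**Conclusion.** The point holds as a minor internal inconsistency. As written, the 6.2.6 instruction is wrong for Step 1 early stoppers and right for Step 2 early stoppers; the likeliest explanation is a mistaken cross-reference. This conclusion needs no numerical assumption.

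Any consequence depends on two events together: a Step 1 participant stops early, and the site gives 6.2.6 precedence over 3.0 and 8.1.1. Only then could the scheduled post-treatment safety visit and Step 1 HCV RNA samples be missed. The first event is unlikely at the documented rate and plausible at the assumed any-reason rates. The second cannot be quantified from the documents. No analysis rule in the SAP relies on the citation.

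**What to change.** In Protocol 6.2.6, cite the Table 6.1-1 post-treatment schedule for participants who stop early in Step 1, and Table 6.1-2 for those who stop early in Step 2. Make the change in both sentences and alter nothing else. A clarification memo is enough, as this study has already used for corrections of similar size. It adds no visits, samples or staff time beyond what 3.0 and 8.1.1 already require, and the SAP needs no revision.
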